## **1. Introduction and Purpose:**

Sepsis is the leading cause of neonatal mortality and every year three million infants die worldwide due to neonatal sepsis (1). In the US, despite significant advances in care, sepsis remains a significant cause of neonatal morbidity and mortality, particularly among Very Low Birthweight (VLBW) preterm infants (PI) (2).

Neonatal early onset sepsis (EOS) is defined as onset of signs and symptoms of sepsis with positive culture <72 hours of age. Compared to term infants, the incidence of EOS is 11 times higher in preterm infants with a mortality rate ranging from 1.5% in term infants to almost 40% in VLBW preterm infants (2).

The diagnosis of neonatal sepsis is challenging, and the prognosis depends on early detection and treatment. The current “gold standard” to diagnose sepsis is a positive blood culture, but there is a variable sensitivity mostly due to inadequate sample volume, transient bacteremia, intrapartum antibiotics and administration of antibiotics before blood sample collection (3,4,5). Although the gold standard for diagnosis of bacterial sepsis is blood culture, only in 25%-40% of blood culture pathogens can be detected (6). Serum markers as IL-6 and CRP have shown to be suitable markers for detecting early onset neonatal sepsis, with a high degree of sensitivity and specificity (18).

In VLBW infants, almost 3 ml of blood is drawn to evaluate EOS for blood culture, CBC and blood group and cross match. This baseline work-up laboratory may represent almost 5-10% total blood volume of a VLBW infant. This iatrogenic acute blood loss may lead to hemodynamic instability and early red blood transfusion in the preterm infant when they are at the highest period risk for intra ventricular hemorrhage (IVH) (23).

The average infant's blood volume is 80ml/kg, while the average blood in the placenta and umbilical cord is 15 to 34 ml/kg which is discarded in the current practice (29). EOS evaluation which includes blood culture, CBC, IT ratio along with biomarkers of EOS like CRP and IL-6 could be done by using placenta/umbilical cord blood (PUCB). PUCB collection is painless, easy and adequate volume may be collected for blood culture. This procedure could decrease iatrogenic blood losses of VLBW infants (23). Currently, there is inadequate published data to support the routine use of PUCB in the evaluation of EOS in VLBW preterm infants.

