## 2.1 *C-Reactive Protein (CRP)*

CRP is one of the most sensitive acute-phase reactants for inflammation. CRP is synthesized by the liver. The CRP response frequently precedes clinical symptoms of sepsis. CRP acts within the humoral immune system, particularly in the detection and clearance of bacterial microorganisms. CRP level increases within 6-18 hours after a stimulus and peaks 8-60 hours later (13). The fetus and newborn synthesize CRP; its level is not affected by gestational age, and CRP does not cross the trans-placental passage of maternal CRP (14).

CRP elevations are nonspecific and may be useful for the detection of systemic inflammatory processes; to assess treatment of bacterial infections with antibiotics. In neonates, CRP has been shown to be more sensitive and specific in diagnosing sepsis than the more commonly used CBC indices (total neutrophil count and I/T ratio) (15). Joram et al found that CRP (cut-off point of 5 mg/dl) measured in umbilical cord blood has a sensitivity, specificity, positive and negative predictive values are respectively 50%, 97%, 67% and 94%. Besides, the same study found that the positive and negative likelihood ratios were 16.7 and 0.5 for CRP (28).

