## **3. Concise Summary of Project:**

Hypothesis: Placental/umbilical cord blood can be used to do early onset sepsis evaluation in low birth weight infants.

Objective: To compare placental/umbilical cord blood and blood from the infant in the evaluation of EOS in VLBW infants.

Specific Aim 1: To compare blood culture, CBC and I/T ratio results of blood from the infant and placental/umbilical cord blood (PUCB).

Objective: All VLBW infants receive empirical broad-spectrum antibiotics after collecting blood for CBC, I/T ratio, and blood culture. We will compare the results of PUCB and blood from the infants, especially comparing white cell count, band count, I/T ratio and if the blood culture is positive or negative. If the blood culture is positive, then we will find out if the micro-organism is the same or not.

Specific Aim 2: To evaluate the role of adding IL-6 and CRP in the evaluation of EOS in VLBW infants.

Objective: We will collect 1 mL of PUCB which will be centrifuged at -40C and serum will be stored at -80 degrees. We will use ELISA to measure IL-6 and CRP. A combination of IL-6 and CRP has been shown to be very helpful in the diagnosis of EOS in VLBW infants. We will also calculate sensitivity, specificity, negative predictive and positive predictive values of IL-6 and CRP individually, as well as, a combination of IL-6 and CRP in the diagnosis of EOS in VLBW infants. We will also find out the duration of antibiotics used in all subjects and find out from IL-6 and CRP data if the antibiotic use was warranted. In future, this may be very useful information in deciding antibiotic duration which will help in avoiding side effects of the unnecessary use of broad-spectrum antibiotics. At present, in our NICU, IL-6 and CRP are not part of EOS evaluation in VLBW infants.

Clinical team will be blinded to the PUCB sepsis evaluation results. In the present study, IL-6 and CRP will not be used clinically but only for research purpose to find out if the addition of IL-6 and CRP help in the management of EOS in VLBW infants.

All VLBW infants get CBC done at admission before starting antibiotics as part of EOS work up. After CBC is done, left over blood sample is saved in the hematology laboratory for 24 hours. We will collect the left-over sample and collect serum after centrifugation. The serum will be saved at -800C for future measurement of IL-6 and CRP. We will compare IL-6 and CRP from infant and PUCB.

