## **13. Potential Benefits:**

There will be no direct benefit to the subjects. But the results of this study may help us to find out if PUCB could be utilized to evaluate EOS in VLBW infants. The results of this study will provide understanding of the utility of PUBC samples to evaluate EOS in VLBW preterm infants. Moreover, this alternative modality of blood analysis could contribute to the prevention of early hemodynamic instability and early blood transfusion in a very high-risk population of VLBW preterm infants. Furthermore, an additional test for sepsis screening as CRP and IL 6, might improve the accuracy for EOS evaluation, and may avoid or prevent unnecessary and prolong antibiotic use in ELBW infants.

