## **14. Biostatistics:**

Statistical analyses will be performed using SPSS 25 for Windows (SPSS Inc., Chicago, IL, USA). Demographic and clinical characteristics will be compared using the non-parametric Mann-Whitney U test, and the results will be presented as medians (range). Categorical variables will be compared using the linear-by-linear association Chi-squared test and will be presented as percentages (%). Receiver operator curve (ROC) analysis will be employed to display the relationship between sensitivity and false positive (FP) rate (1-specificity) and to select the best cut-off value for umbilical cord IL-6 and CRP to predict EOS. Data will be as adjusted by gestational age at delivery, administration of prenatal corticosteroids and antibiotics. Differences will be considered statistically significant at a confidence level of  $p < 0.05$  with two-sided alternative hypotheses

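### Aim 2 judges whether antibiotics were warranted from IL-6 and CRP alone, the tests under evaluation, so that one verdict is circular and could mislabel courses in either direction

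*Combined protocol and SAP*

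**What the plan says.** Section 3 of the combined protocol and SAP gives Specific Aim 2 as "To evaluate the role of adding IL-6 and CRP in the evaluation of EOS in VLBW infants". Under it the team will "calculate sensitivity, specificity, negative predictive and positive predictive values of IL-6 and CRP individually", and for the two combined, in the diagnosis of EOS. The next sentence turns to treatment: antibiotic duration will be recorded for every subject, and the team will "find out from IL-6 and CRP data if the antibiotic use was warranted". The aim adds that this may later help in deciding how long to give antibiotics. Section 13 offers a related benefit, that the markers "might improve the accuracy for EOS evaluation" and may reduce unnecessary treatment.

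EOS itself is "defined as onset of signs and symptoms of sepsis with positive culture <72 hours of age" (section 1), a definition that uses neither marker. Section 14 will use ROC curves "to select the best cut-off value for umbilical cord IL-6 and CRP to predict EOS". No section says what marker result makes a course warranted, whether one or both markers must be positive, or how culture or clinical findings enter that judgement.

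**The concern.** A test cannot be validated by a standard made from the same test. If need for antibiotics is read off IL-6 and CRP, a marker-negative infant counts as unnecessarily treated by construction, whatever the culture showed, and a marker-positive infant counts as correctly treated. The resulting share of unwarranted courses restates the share of marker-negative infants. It carries no evidence that those infants could have gone without treatment.

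The number matters because it is the one the aim links to future antibiotic duration. The verdict would also rest on thresholds picked from the same infants, since section 14 chooses the cut-offs by ROC in the study data.

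**Working it through.** **1. Where the circularity lies.** Set the two Aim 2 analyses side by side. The accuracy analysis compares the markers with EOS, which section 1 defines by clinical signs and culture, so its reference lies outside the markers. The verdict on antibiotics compares treatment with the markers and names no other reference. Only the second is circular.

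**2. Inputs.**
- Sample size: 63 (section 3, power analysis).
- Cord CRP, section 2.1: "measured in umbilical cord blood has a sensitivity, specificity, positive and negative predictive values are respectively 50%, 97%, 67% and 94" per cent.
- Cord IL-6, section 2.2: sensitivity 87% and specificity 90% in term and preterm infants together; 96% and 94% in preterm infants only; another cited study gives 100% sensitivity with early measurement.
- IL-6 and CRP complementing each other, section 2.3: cited sensitivity 100%.
- EOS prevalence in this cohort: not given. I assume 1% to 10% and show the range.
- For combined rules I assume that the two markers are independent given EOS status.

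**3. Check on the cited CRP figures.** The plan gives no figure for the verdict itself, so I checked the CRP inputs. Solving the positive predictive value for prevalence gives 0.67 × 0.03 / (0.67 × 0.03 + 0.50 × 0.33) = 0.0201 / 0.1851 = 10.9%. At that prevalence the negative predictive value is 0.97 × 0.891 / (0.97 × 0.891 + 0.50 × 0.109) = 94.1%, as cited. The four figures agree with one another. The 10.9% describes the cited study's sample, not this cohort.

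**4. Combined rules.**
- Either marker positive: sensitivity 1 − 0.50 × 0.13 = 93.5%, or 1 − 0.50 × 0.04 = 98%; specificity 0.97 × 0.90 = 87.3%, or 0.97 × 0.94 = 91.2%.
- Both markers positive: sensitivity 0.50 × 0.87 = 43.5%, or 0.50 × 0.96 = 48%; specificity 1 − 0.03 × 0.10 = 99.7%, or 1 − 0.03 × 0.06 = 99.8%.

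**5. Expected mislabelled infants among 63.** With prevalence p:
- true EOS called not warranted = 63 × p × (1 − sensitivity);
- no EOS called warranted = 63 × (1 − p) × (1 − specificity).

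Example, CRP alone at p = 5%: 63 × 0.05 × 0.50 = 1.6 and 63 × 0.95 × 0.03 = 1.8.

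| Rule | EOS called not warranted, p = 1% / 5% / 10% | No EOS called warranted, p = 1% / 5% / 10% |
|---|---|---|
| CRP alone | 0.32 / 1.58 / 3.15 | 1.87 / 1.80 / 1.70 |
| IL-6 alone, 87% and 90% | 0.08 / 0.41 / 0.82 | 6.24 / 5.98 / 5.67 |
| IL-6 alone, 96% and 94% | 0.03 / 0.13 / 0.25 | 3.74 / 3.59 / 3.40 |
| Either positive, IL-6 at 87% and 90% | 0.04 / 0.20 / 0.41 | 7.92 / 7.60 / 7.20 |
| Either positive, IL-6 at 96% and 94% | 0.01 / 0.06 / 0.13 | 5.50 / 5.28 / 5.00 |
| Both positive, IL-6 at 87% and 90% | 0.36 / 1.78 / 3.56 | 0.19 / 0.18 / 0.17 |
| Both positive, IL-6 at 96% and 94% | 0.33 / 1.64 / 3.28 | 0.11 / 0.11 / 0.10 |

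On the cited 100% sensitivities the first error is zero. The share of true EOS courses called not warranted therefore runs from 0% to 56.5% (1 − 0.435), depending on the unstated rule. At p = 5% the chance of at least one such course is 1 − (1 − 0.05 × 0.50)^63 = 80% for CRP alone, and 6% to 19% if either marker counts.

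**The case against.** The strongest reply is that the markers are properly tested elsewhere. Aim 2 and section 14 plan accuracy measures and ROC analysis against EOS, and an EOS case with negative markers is a false negative in that table. That stands. A reader might infer that the benefit of the markers is assumed and never tested, or that missed sepsis would be hidden; the documents support neither reading.

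A reader might also infer that the verdict is biased towards calling treatment unnecessary, or that it is bound to mislabel true EOS. Neither follows. With IL-6 alone, or with either marker counting, the expected error is mainly the other way. This holds even at the cited CRP study's 10.9%: IL-6 gives 56.1 × 0.06 to 0.10 = 3.4 to 5.6 infants without EOS called warranted, against 6.87 × 0.04 to 0.13 = 0.3 to 0.9 EOS cases called not warranted. The direction towards not warranted appears only with CRP alone, at the higher assumed prevalences, or if both markers must be positive, and the plan states no rule.

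The sponsor could add that culture is a poor standard, since by section 1 "only in 25%-40% of blood culture pathogens can be detected". That is a fair limit on any culture-based reference. It argues for showing culture-negative infants separately and does not justify letting the index tests judge themselves.

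Finally, the stakes are limited. Section 3 says that the marker results will not be used in care, and the language about future use is hedged.

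**Conclusion.** The point holds for the verdict on antibiotic use and for nothing wider. As written, that verdict takes IL-6 and CRP as its only arbiter, so it cannot show that they identify avoidable treatment or support later decisions on duration.

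Its size and direction depend on the marker rule. In 63 infants at an assumed prevalence of 1% to 10%, true EOS courses called not warranted number about 0.3 to 3.2 with CRP alone, fewer than 0.5 if either marker counts, and none on the cited 100% sensitivities. Infants without EOS called warranted number about 3 to 6 with IL-6 alone. These counts rest on the assumed prevalence, on accuracy figures carried over from the cited studies and, for combined rules, on conditional independence. The circularity rests on none of them. It is worth correcting before analysis; the accuracy analyses and clinical care are not affected by it.

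**What to change.** Replace the sentence in Aim 2. Classify each infant by the section 1 EOS definition, without reference to IL-6 or CRP, and state that the culture meant is the infant's own, since the definition does not name the sample. Then cross-tabulate antibiotic-days by EOS status and marker status for IL-6, CRP and the combination, with the combination rule stated in advance. Report:

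- antibiotic-days in EOS-negative, marker-negative infants, as potentially avoidable;
- the number of EOS-positive, marker-negative infants, as cases that the markers would have missed;
- exact or bootstrap confidence intervals for both.

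Label the result exploratory, and show culture-negative infants given extended courses on a separate line because the protocol itself calls culture insensitive. Expect wide intervals: 5% prevalence means about 3 EOS cases (63 × 0.05 = 3.15), and even 3 of 3 detected has an exact 95% lower limit of 0.025^(1/3) = 29%.

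The cost is a short text change and one table from data already to be collected, with no new samples. What remains is an imperfect reference, which the separate line makes visible.

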#### *Routine management of VLBW infants in NICU at UTMB Galveston:*

In NICU at UTMB Galveston, routinely, all VLBW infants admitted to NICU get sepsis evaluation by collecting blood from infant for CBC, I/T ratio, and blood culture followed by a course of empiric antibiotics for 2 – 3 days. This requires almost 2 – 3 mL of blood volume which may be up to 5% blood loss in an extremely premature infant which may lead to hemodynamic instability and anemia, resulting in the requirement for blood transfusion. If the sepsis evaluation is not conclusive, then the course of antibiotics may be extended to 3 to 7 days. Addition of CRP and IL-6 in EOS evaluation may be helpful in determining the duration of antibiotics. However, in NICU at UTMB Galveston, CRP and IL-6 are not part of EOS evaluation.

#### *Placenta/Umbilical Cord blood (PUCB):*

In the current research project, we want to use PUCB to do sepsis evaluation in VLBW infants. There is approximately 15 – 20 mL/kg blood in the placenta and umbilical cord. That means in VLBW infants (<34 w) there will be approximately 15 – 20 mL blood in the placenta and umbilical cord which is fetal blood hence it can be utilized to do EOS sepsis evaluation. This

will save blood in VLBW infants. As blood in PUCB is nothing but fetal blood. There is a misconception that fetal and maternal blood is mixed in the placenta. Actually, there is no mixing of maternal and fetal blood in the placenta. After birth, the placenta and umbilical cord are discarded along with the blood inside. We want to utilize fetal blood in the placenta/umbilical cord for the evaluation of EOS in VLBW infants.

The current research project will evaluate the utility of PUCB to assess early onset sepsis (EOS) in VLBW infants (<34 weeks). This study will not affect the management of the infants at all. The lab tests will be done in blocks and hence the results will not be available in real time. The clinical management of infants will be decided by the neonatal team taking care of the infants. The neonatologists will continue to treat infants as per the NICU protocol.

We will compare blood culture, CBC, and I/T ratio results from the infant and PUCB. We will calculate the sensitivity, specificity, positive and negative predictive value of these tests in the evaluation of EOS.

During hospital stay, all VLBW infants get CBC done immediately after birth. After CBC is done, the left-over sample is stored in the hematology laboratory for 24 hours. After 24 hours, this blood sample is discarded. We will collect left over blood from the hematology laboratory to extract serum by centrifuging the blood sample. The serum will be stored at -80°C for future measurements of CRP and IL-6. We will also compare CRP and IL-6 levels in placenta/umbilical cord blood and discarded infant blood. Additionally, we will evaluate the role of adding IL-6 and CRP in the evaluation of EOS in VLBW infants.

#### *Power analysis:*

In order to do a power analysis to determine sample size, an estimate of effect size was based upon the Rashawn et al (30) study which found significant correlations of CRP with other biomarkers.

In G\*Power (31) the following was used:

- Effect size of  $r=.4$
- Alpha=.05
- Power (1-alpha)=.95
- Yielding a sample size of 63

To accomplish this project, a cohort of preterm infants will be recruited from the infants admitted to the NICU at UTMB, Galveston. We routinely admit around 80 infants/year who are <34 weeks' gestation. We expect to recruit about 50 – 60% VLBW infants born in UTMB, Galveston in the current study. Therefore, we hope to recruit our desired sample size (n=63) in about 18 months.

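### The power statement for n=63 concerns a non-zero correlation that neither aim nor Section 14 plans to test, and its 95% holds only one-sided (about 91% under the stated two-sided testing)

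*Combined protocol and SAP*

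**What the plan says.** The only sample-size justification is the Power analysis in Section 3. Its effect size, r=.4, rests on an external "study which found significant correlations of CRP with other biomarkers". With alpha .05 and "Power (1-alpha)=.95", the calculation is reported as "Yielding a sample size of 63". The paragraph does not say which two measurements are to be correlated in this trial, or whether the test is one- or two-sided.

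The study's questions are stated elsewhere in Section 3:

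- Aim 1: "To compare blood culture, CBC and I/T ratio results of blood from the infant and placental/umbilical cord blood (PUCB".
- Aim 2: "To evaluate the role of adding IL-6 and CRP in the evaluation of EOS in VLBW infants", with the quantities to be estimated given as "We will also calculate sensitivity, specificity, negative predictive and positive predictive values of IL-6 and CRP individually" and in combination.
- A further comparison with no method named: "We will compare IL-6 and CRP from infant and PUCB". The PUCB subsection of Section 3 repeats it for the levels of both markers.

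Section 14 lists Mann-Whitney tests, a linear-by-linear chi-squared test for categorical variables, ROC analysis to choose cut-offs for cord IL-6 and CRP, and adjustment for covariates. Significance is judged at p<0.05 "with two-sided alternative hypotheses".

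**The concern.** A power figure applies to one test of one hypothesis. Here the hypothesis is that some correlation is zero, and that test is not among the planned analyses. The planned work is a paired comparison of two blood sources and an assessment of accuracy against EOS. The information 63 infants give on these depends on other quantities: the spread of the within-infant differences for the first, and the number of EOS cases for the second. The plan uses neither in setting n.

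The stated 95% also looks inconsistent with the two-sided rule in Section 14. The protocol's only quantitative assurance would then be too favourable for its own test and silent on both aims. This matters because Sections 3 and 13 link the results to future decisions on antibiotic use.

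**Working it through.** **Inputs.** r=.4, alpha=.05, power=.95 and n=63 (Section 3, Power analysis); two-sided testing (Section 14).

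**1. Reproducing 63.** The Fisher-z approximation for a test of zero correlation is n = ((z_alpha + z_power)/atanh(r))² + 3, with atanh(.4) = 0.4236.

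- One-sided: ((1.645 + 1.645)/0.4236)² + 3 = 63.3. The exact bivariate-normal distribution of r gives n=63, with power 95.2%.
- Two-sided: ((1.960 + 1.645)/0.4236)² + 3 = 75.4. The exact calculation gives n=75, with power 95.1%.
- A point-biserial correlation would give 59 one-sided and 71 two-sided.

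Of these variants, only the one-sided bivariate correlation gives 63.

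**2. Power at n=63 under Section 14.** The exact two-sided power for r=.4 is 91.1%.

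**3. What a significant result would show.** With 61 degrees of freedom the two-sided critical t is 2.00. The smallest significant correlation is 2.00/sqrt(2.00² + 61) = 0.248. A PUCB-infant correlation only a little above 0.25 would therefore be declared significant. Correlation is also unaffected by a constant shift between the two sources, so the test cannot establish agreement.

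**4. What 63 complete pairs give for the paired comparison.** Let SD be the standard deviation of the paired difference.

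- Mean difference: 95% CI half-width = t(62)/sqrt(63) = 2.00/7.94 = 0.25 SD.
- Each 95% limit of agreement: half-width ≈ t(62) × sqrt(3/63) = 2.00 × 0.218 = 0.44 SD.
- Culture agreement: if all 63 pairs agree, the exact lower 95% limit is 0.025^(1/63) = 94.3%.

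These are best cases. Section 4 draws infant serum from blood left over after the CBC, so there may be fewer complete pairs for CRP and IL-6.

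**5. What the study gives for sensitivity.** The documents state no EOS rate for this cohort, so the case count must be assumed. If all k cases are detected, the exact lower 95% limit is 0.025^(1/k):

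| Assumed EOS cases | 95% CI if all are detected |
|---|---|
| 3 | 29% to 100% |
| 6 | 54% to 100% |
| 7 | 59% to 100% |

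Two reference points, both assumptions, show how uncertain the count is:

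- A 1% rate gives 63 × 0.01 = 0.6 expected cases and a 0.99^63 = 53% chance of none.
- The cord-CRP figures in Section 2.1 (sensitivity 50%, specificity 97%, PPV 67%) imply a prevalence p with 0.67 = 0.50p/(0.50p + 0.03(1 − p)). Then p = 0.0201/0.1851 = 10.9%, or about 7 cases in 63. That is another study's population.

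**The case against.** The best defence is that a PUCB-infant correlation of CRP or IL-6 was intended. The paragraph takes only the size of r from the external study, and Section 3 does plan to compare those levels between the two sources. This stands in part. A reader might infer that 63 was computed for CRP against other biomarkers, but the documents do not say so; the pair is simply not named. The defence still does not rescue the calculation, because no such correlation appears in Section 14 and a non-zero r would not show agreement.

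A second defence is that Section 14 does contain a correlation-type test: the linear-by-linear chi-squared statistic equals (N−1)r². True, but it is planned for categorical variables, not for biomarker levels.

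Third, the Power analysis openly states its r and alpha, and it does not claim 95% power for accuracy. The study is observational, and its results do not reach the clinical team. This also stands, and it limits the harm to how the results are read. It does not supply a basis for either aim.

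Finally, Aim 1 speaks of comparing, not of agreement, and the plan never mentions limits of agreement. They are offered here as one suitable way to express precision, not as something the plan promised.

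**Conclusion.** The power statement is wrong as written in one figure and does not bear on the study's questions. For r=.4 and 63 infants, power is about 91% under the plan's two-sided testing; the stated 95% is the one-sided value, and two-sided 95% would need 75. These results assume bivariate normality and nothing outside the documents. Separately, no passage gives a sample-size or precision basis for the paired comparison or for diagnostic accuracy. The label 1-alpha for power is a slip without numerical effect, since alpha and beta are both .05 here.

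Three stronger readings are not supported:

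- **That the two sources are not interchangeable.** With a true PUCB-infant correlation of .4 and equal SDs, limits of agreement would be ±1.96 × sqrt(2 × 0.6) = ±2.15 between-infant SDs. But .4 is a planning value, and the plan states no acceptable difference.
- **That about 0.6 to 7 EOS cases are to be expected.** The lower figure is a pure assumption. The upper one is borrowed from another population and is not a bound for this cohort.
- **That 75 infants must be recruited.** That follows only if 95% power for this correlation is to be kept, and the correlation serves neither aim.

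**What to change.** In the Power analysis of Section 3:

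- Restate the power as about 91%, two-sided, for r=.4 at n=63, and correct the label to 1-beta.
- Name the two variables to which r refers.
- State that this figure gives no power for Aim 1 or for the Aim 2 accuracy estimates.

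Then add the precision available for the planned comparisons, based on the number of complete pairs (at most 63):

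- The CI for the paired PUCB-infant difference, or the limits of agreement (each known to about ±0.44 SD of the paired difference at 63 pairs), on a suitable scale such as log for CRP and IL-6.
- Exact CIs for culture agreement.
- Exact CIs for sensitivity over a range of EOS case counts explicitly labelled as assumed, for example 29–100% with 3 cases and 59–100% with 7 if all are detected.

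Label the Aim 2 accuracy and cut-off estimates exploratory.

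The cost is protocol wording only, with no change in n. The downside is that the stated figure becomes less favourable.

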## **9. Recruitment Methods and Consenting Process:**

### *Recruitment*

All eligible infants born at UTMB Galveston will be recruited in the study. We expect 50 - 60% success in the recruitment after accounting for exclusion criteria and timing of delivery. If the infant is born after hours, the research team may not be available to collect the PUCB sample. We admit around 80 infants/year who are <34 weeks' gestation. We hope to recruit our desired sample size (n=63) in 18 months.

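### The sample size of 63 gives 95% power only for a one-sided test; under the plan's two-sided rule the power is about 91%

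*Combined protocol and SAP*

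**What the plan says.** The power analysis in Section 3 of the combined protocol and SAP bases its effect size on a cited "study which found significant correlations of CRP with other biomarkers". The G*Power inputs are a correlation of 0.4, alpha of 0.05 and a power entry that reads "Power (1-alpha)=.95". The result is "Yielding a sample size of 63". Neither the sidedness of the test nor the G*Power procedure is given.

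Section 14 (Biostatistics) contains the only general testing rule in the document: significance at p < 0.05 "with two-sided alternative hypotheses". Section 9 carries the number forward as the recruitment target: "We hope to recruit our desired sample size (n=63) in 18 months".

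**The concern.** The same alpha of 0.05 gives different sample sizes for one-sided and two-sided tests. A two-sided test puts 0.025 in each tail, so it has a higher critical value and needs more subjects for the same power. If 63 came from a one-sided calculation and the study tests two-sided, the stated 95% power is not delivered.

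This calculation is the only justification of sample size in the protocol, and 95% is the only operating characteristic it states. The power label adds to the doubt. Power is one minus the type II error (1 − beta). Because alpha is 0.05, 1 − alpha also equals 0.95, so a reader cannot be sure that 0.95 was a deliberate power target.

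**Working it through.** **Inputs.** From the Section 3 power analysis: ρ = 0.4 (against 0), alpha = 0.05, power = 0.95, n = 63. From Section 14: two-sided testing at 0.05.

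**Step 1. Exact test, bivariate normal model.** The null is rejected when the sample correlation exceeds r_c = t / √(t² + n − 2). Here t is the 1 − alpha quantile (one-sided) or 1 − alpha/2 quantile (two-sided) of Student's t on n − 2 degrees of freedom. Power is the probability, under ρ = 0.4, that the sample correlation falls in the rejection region. It was found by integrating the exact density of r.

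At n = 63 (61 degrees of freedom):
- One-sided: t = 1.670, r_c = 1.670 / √(1.670² + 61) = 0.209.
- Two-sided: t = 2.000, r_c = 2.000 / √(2.000² + 61) = 0.248.

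| n | One-sided power | Two-sided power |
|---|---|---|
| 62 | 0.949 | – |
| 63 | **0.952** | **0.911** |
| 74 | – | 0.949 |
| 75 | – | **0.951** |

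The plan's 63 is reproduced exactly as the smallest one-sided n that reaches 95%. The two-sided minimum is 75.

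**Step 2. Check by Fisher's z.** n = [(z_alpha + z_power) / atanh(0.4)]² + 3, with atanh(0.4) = 0.4236.
- One-sided: [(1.645 + 1.645) / 0.4236]² + 3 = 63.3.
- Two-sided: [(1.960 + 1.645) / 0.4236]² + 3 = 75.4.
- Two-sided power at 63: Φ(0.4236 × √60 − 1.960) = Φ(1.322) = 0.907.

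**Step 3. Other models.** A simulation of 200,000 samples of 63 gave 95.2% one-sided and 91.1% two-sided. The point-biserial model needs 59 one-sided or 71 two-sided, so it does not yield 63; its two-sided power at 63 is 92.6%. Across all the methods tried, the two-sided n runs from 71 to 76 and the two-sided power at 63 from 90.7% to 92.6%.

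**Step 4. Size of the gap.**
- Power: 95.0% − 91.1% = 3.9 percentage points.
- Type II error: 8.9% against 5%, a ratio of 1.8.
- Sample size: 75 − 63 = 12 more infants, or 12/63 = 19%.
- Correlation detectable with 95% two-sided power at n = 63: 0.432. At exactly 0.430 the power is 94.8%.

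**Step 5. Feasibility on the plan's own figures.** Sections 3 and 9 give about 80 infants a year, 50–60% recruited, over 18 months: 80 × 1.5 = 120, and 50–60% of 120 is 60 to 72. The target of 63 lies inside this range; 75 lies outside it.

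**The case against.** The strongest reply has three parts.

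First, the document never says that the calculation was one-sided. That is correct, and it is inferred here because 63 matches the one-sided exact answer and no two-sided variant tried comes below 71. The shortfall does not rest on the inference: however 63 was obtained, it gives about 91% power at r = 0.4 under a two-sided 0.05 test.

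Second, Section 14 lists Mann-Whitney, linear-by-linear chi-squared and ROC analyses but no correlation test, so its two-sided rule reaches the powered test only by default. This also stands. But it is the only testing rule in the plan, and a one-sided exception would have to be written down. The text needs an edit either way.

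Third, the practical effect is small. Power of 91% is still high; a two-sided target of 90% needs only 61 infants, fewer than planned. No analysis or design decision changes, and clinicians are blinded to the cord-blood results. This stands, and it limits the importance of the point without making the stated figure right. Similarly, the 1 − alpha label is probably a slip, since alpha is listed separately, and it does not alter n.

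Whether a correlation is a suitable basis for sizing a study whose aims are comparison of blood sources and diagnostic accuracy is a separate question. Correcting the power figure does not answer it.

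**Conclusion.** The concern holds. Under the two-sided rule in Section 14, 63 infants give 91.1% power to detect a correlation of 0.4, not 95%, and 95% power needs 75. The power label is also wrong.

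The result assumes a bivariate normal test of a correlation against zero, the general two-sided rule applied to that test, and usable paired values from all 63 infants. The plan makes no allowance for missing or unusable samples, and any loss would lower the power further. The error is definite, but its practical effect is modest.

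**What to change.** Keep n = 63 and replace the stated result in the Section 3 power analysis with a sentence such as:

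> A sample of 63 infants gives 91% power (1 − beta) to detect a correlation of 0.40 with a two-sided test at the 0.05 level; 95% power corresponds to a correlation of about 0.43.

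Correct the label from 1 − alpha to 1 − beta in the same place, and name the G*Power procedure so that the figure can be reproduced. The recruitment target in Section 9 can stay as it is.

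The cost is one sentence and a slightly less favourable stated power; no extra infants are needed. If the sponsor wishes to keep 95% power at r = 0.4 two-sided, the alternative is 75 infants. That exceeds the 60 to 72 implied by the plan's recruitment figures over 18 months, so restating the power is the more realistic choice. If a one-sided test was intended, Section 14 must say so and justify it.
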